6.4 Duration of Therapy

Treatment may continue for up to 12 months (maximum 12 doses) or until one of the criteria for durvalumab discontinuation is met.

Permanent discontinuation of durvalumab

An individual subject will not receive any further investigational product if any of the following occur in the subject in question:

- Confirmation of PD and investigator determination that the subject is no longer benefiting from treatment with durvalumab
- Withdrawal of consent or lost to follow-up
- Adverse event that, in the opinion of the investigator or the sponsor, contraindicates further dosing
- Subject is determined to have met one or more of the exclusion criteria for study participation at study entry and continuing investigational therapy might constitute a safety risk
- Pregnancy or intent to become pregnant
- Any AE that meets criteria for discontinuation as defined in Appendix D.
- Grade \geq 3 infusion reaction
- Subject noncompliance that, in the opinion of the investigator or sponsor, warrants withdrawal; eg, refusal to adhere to scheduled visits

HCC #:16-054

Version Date: 008/11/2020

- Initiation of alternative anticancer therapy including another investigational agent

Subjects who are permanently discontinued from further receipt of investigational product, regardless of the reason (withdrawal of consent, due to an AE, other), will be identified as having permanently discontinued treatment.

Subjects who are permanently discontinued from receiving investigational product will be followed for safety per Appendix E or F, unless consent is withdrawn or the subject is lost to follow-up or enrolled in another clinical study. All subjects will be followed for survival. Subjects who decline to return to the site for evaluations will be offered follow-up by phone at months 2, 3, 4, 6, 8, 10, 12 after stopping treatment, and then every 2 months after that as an alternative.

Withdrawal of consent

If consent is withdrawn, the subject will not receive any further investigational product or further study observation.

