8.3.4.2 Hepatic function abnormality

Hepatic function abnormality (as defined in Section 8.1.6 in a study subject, with or without associated clinical manifestations, is required to be reported as "hepatic function abnormal" **within 24 hours of knowledge of the event** to the sponsor and AstraZeneca/MedImmune Patient Safety using the designated Safety e-mailbox (see Section 8.3.2 for contact information), unless a definitive underlying diagnosis for the abnormality (e.g., cholelithiasis or bile duct obstruction) that is unrelated to investigational product has been confirmed.

- If the definitive underlying diagnosis for the abnormality has been established and is unrelated to investigational product, the decision to continue dosing of the study subject will be based on the clinical judgment of the investigator.

HCC #:16-054

Version Date: 008/11/2020

- If no definitive underlying diagnosis for the abnormality is established, dosing of the study subject must be interrupted immediately. Follow-up investigations and inquiries must be initiated by the investigational site without delay.

Each reported event of hepatic function abnormality will be followed by the investigator and evaluated by the sponsor and AstraZeneca/MedImmune.

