	Grade 2 (AST or ALT > 3 to 5 times ULN and/or TB >1.5-3.0 times ULN)	Hold Study drug/study regimen dose until grade 2 resolution to ≤ Grade 1 •If toxicity worsens then treat as Grade 3 or Grade 4 •If toxicity improves to grade ≤1 or baseline, resume study drug/study regimen after	For Grade 2 AST or ALT and or TB elevation : 
 - Regular and frequent checking of LFTs (e.g. every 1-2 days) until elevations of these are improving or resolved. - If no resolution to ≤ Grade 1 in 1-2 days, discuss with study physician. - If event is persistent (> 3-5 days) or worsens, promptly start prednisone 1-2mg/kg/day or IV equivalent. - If still no improvement within 3-5 days despite 1-2mg/kg/day of prednisone or IV equivalent, consider additional workup and prompt treatment with IV methylprednisolone 2-4mg/kg/day started. - If still no improvement within 3-5 days despite 2-4mg/kg/day of IV methylprednisolone, promptly start immunosuppressives (mycophenolate mofetil)¹ . Discuss with study physician if

Table 1- Immune-Mediated Reactions (continued)			
		Dose Modifications	Toxicity Management
		completion of steroid taper.	
mycophenolate mofetil is not available. Infliximab should NOT be used.
 
 – Once improving, gradually taper steroids over ≥ 28 days and consider prophylactic antibiotics, antifungals and anti PCP treatment (please refer to current NCCN guidelines for treatment of cancer-related infections [Category 2B recommendation])

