	Grade 3 (AST or ALT > 5 -20 times ULN and/or TB > 3.0 -10 times ULN	
For elevations in transaminases $\leq 8 \times$ ULN, or elevations in bilirubin $\leq 5 \times$ ULN
 
Hold study drug/study regimen dose until resolution to \leq Grade 1 or baseline
 
Resume study drug/study regimen if elevations downgrade \leq Grade 1 or baseline within 14 days and after completion of steroid taper.
 
Permanently discontinue study drug/study regimen if the
	
For Grade 3 or 4 AST or ALT and/or TB elevation:
 
 – Promptly initiate empiric IV methylprednisolone at 1 to 4 mg/kg/day or equivalent – If still no improvement within 3-5 days despite 1 to 4 mg/kg/day methylprednisolone IV or equivalent, promptly start treatment with immunosuppressive therapy (mycophenolate mofetil) Discuss with study physician if mycophenolate is not available. Infliximab should NOT be used. – Hepatology consult, abdominal workup, and imaging as appropriate. – Once improving, gradually taper steroids over ≥ 28 days and consider prophylactic antibiotics, antifungals and anti PCP treatment (please refer to current NCCN guidelines for treatment of cancer-related infections [Category 2B recommendation])

Table 1- Immune-Mediated Reactions (continued)			
		Dose Modifications	Toxicity Management
		
elevations do not downgrade to \leq Grade 1 or baseline within 14 days
 
For elevations in transaminases $> 8 \times$ ULN or elevations in bilirubin $> 5 \times$ ULN, discontinue study drug/study regimen
 
Permanently discontinue study drug/study regimen for any case meeting Hy's law criteria (ALT $> 3x$ ULN + bilirubin $> 2x$ ULN without initial findings of cholestasis (i.e. elevated alkaline P04) and in the absence of any alternative cause
	

Table 1- Immune-Mediated Reactions (continued)			
		Dose Modifications	Toxicity Management
	Grade 4 (AST or ALT > 20 times ULN and/or TB > 10 times ULN)	Permanently discontinue study drug/study regimen	

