	Grade 2	
Hold study drug/study regimen dose until resolution to \leq Grade 1
 
Permanently discontinue study drug/study regimen if it does not resolve to \leq Grade 1 within 30 days or if there are signs of respiratory insufficiency or autonomic instability
	
Grade 2
 
 - Discuss with the study physician - Care should be taken to monitor patients for sentinel symptoms of a potential decompensation as described above - Obtain a Neurology Consult - Sensory neuropathy/neuropathic pain may be managed by appropriate medications (e.g., gabapentin, duloxetine, etc.) 
MYASTHENIA GRAVIS
 
 o Steroids may be successfully used to treat Myasthenia Gravis. Important to consider

Table 1- Immune-Mediated Reactions (continued)			
		Dose Modifications	Toxicity Management
			
that steroid therapy (especially with high doses) may result in transient worsening of myasthenia and should typically be administered in a monitored setting under supervision of a consulting neurologist.
 
 ○ Patients unable to tolerate steroids may be candidates for treatment with plasmapheresis or IV IG. Such decisions are best made in consultation with a neurologist, taking into account the unique needs of each patient. ○ If Myasthenia Gravis-like neurotoxicity present, consider starting acetylcholine esterase (AChE) inhibitor therapy in addition to steroids. Such therapy, if successful, can also serve to reinforce the diagnosis. 
GUILLAIN-BARRE:
 
 ○ Important to consider here that the use of steroids as the primary treatment of Guillain-Barre is not typically considered effective. Patients requiring treatment should be started with IV IG and followed by

Table 1- Immune-Mediated Reactions (continued)			
		Dose Modifications	Toxicity Management
			plasmapheresis if not responsive to IV IG.

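### The Hy's-law permanent stop in Appendix D is printed only in the Grade 3 hepatitis cell, while the overlapping Grade 2 row says hold then resume with no exception or cross-reference

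*Combined protocol and SAP*

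**What the plan says.** The relevant text is spread over four places.

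- **Appendix D, Table 1, Hepatitis, Grade 3 cell.** After the hold and discontinue branches comes the instruction "Permanently discontinue study drug/study regimen for any case meeting Hy's law criteria". A parenthesis defines these as ALT above 3 times ULN plus bilirubin above 2 times ULN, without initial cholestasis and with no alternative cause.
- **Appendix D, Table 1, Hepatitis, Grade 2 row.** The band is "Grade 2 (AST or ALT > 3 to 5 times ULN and/or TB >1.5-3.0 times ULN". The drug is held, and then "If toxicity improves to grade ≤1 or baseline, resume study drug/study regimen after" completion of the steroid taper. The only escalation in the dosing cell is to treat as Grade 3 or 4 if the toxicity worsens. The management cell adds "If no resolution to ≤ Grade 1 in 1-2 days, discuss with study physician". Hy's law is not mentioned.
- **Section 6.4.** The grounds on which a subject receives no further drug include "Any AE that meets criteria for discontinuation as defined in Appendix D".
- **Sections 8.1.6 and 8.3.4.2.** ALT or AST above 3 times with bilirubin above 2 times ULN is a hepatic function abnormality, reportable within 24 hours unless an unrelated diagnosis is confirmed. On dosing, 8.3.4.2 says "If no definitive underlying diagnosis for the abnormality is established, dosing of the study subject must be interrupted immediately". It also says "Each reported event of hepatic function abnormality will be followed by the investigator and evaluated by the sponsor and AstraZeneca/MedImmune". Section 8.1.6 makes Hy's-law cases reportable as SAEs. Neither section states a permanent stop.

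**The concern.** Appendix D is laid out to be used by grade: find the toxicity, find the grade, follow the row. A stop meant for every case but printed in one grade's cell can be missed by someone who correctly follows another row. Here the missed instruction concerns suspected drug-induced liver injury, and the error would be to give durvalumab again to a patient whom the protocol intends to stop for good.

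Only patient safety is at stake. The point does not bear on the overall survival estimate or on the sample size.

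**Working it through.** There is no planned figure to reproduce. The check is whether the Hy's-law thresholds fall inside a grade band whose row gives a different instruction. All values are multiples of ULN.

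**1. Bands from the hepatitis rows of Appendix D, Table 1**

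| Grade | ALT/AST | Bilirubin | Dosing instruction |
|---|---|---|---|
| 1 | >1 to 3 | >1 to 1.5 | none |
| 2 | >3 to 5 | >1.5 to 3.0 | hold, then resume |
| 3 | >5 to 20 | >3.0 to 10 | hold or discontinue by level; Hy's-law stop |
| 4 | >20 | >10 | permanent stop |

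**2. Overlap of the Hy's-law thresholds (ALT >3 and bilirubin >2) with each grade**

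- Grade 1: none, because neither test can exceed its threshold.
- Grade 2: ALT (3, 5] with >3 leaves (3, 5]. Bilirubin (1.5, 3.0] with >2 leaves (2, 3.0]. The overlap is ALT >3 to 5 with bilirubin >2 to 3.
- Grade 3: there is overlap, but the stop is printed in the same cell.
- Grade 4: a permanent stop applies anyway.

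The exposed region is therefore the Grade 2 box only.

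**3. One patient, two instructions.** Take ALT 4 and bilirubin 2.5, no initial cholestasis, no other cause. ALT lies between 3 and 5, so Grade 2. Bilirubin lies between 1.5 and 3.0, so Grade 2. Both Hy's-law thresholds are exceeded (4 > 3 and 2.5 > 2). The Grade 2 row ends in resumption. The sentence in the Grade 3 cell, taken with 6.4, ends in permanent discontinuation.

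**4. How the table handles other stops that cross grades**

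- Failure to reduce corticosteroid to 10 mg prednisone a day within 12 weeks: printed once, in the overall section at the top of Table 1.
- Bullous skin formation: printed once, in the rash Any Grade row, in capitals.
- Neuromotor syndromes: the stop "within 30 days or if there are signs of respiratory insufficiency or autonomic instability" appears in both the Grade 2 and the Grade 3 cell.
- Hy's law: it is absent from the overall section, the hepatitis Any Grade row and the Grade 2 row.

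**5. The Grade 3 branches, a separate and lesser matter.** As printed, the hold branch covers transaminases ≤8 *or* bilirubin ≤5, and the discontinue branch covers transaminases >8 *or* bilirubin >5. When exactly one limit is exceeded and the other test is raised but within its limit, both apply. With ALT 10 and bilirubin 4, 4 ≤ 5 satisfies hold and 10 > 8 satisfies discontinue. If each limit is read as applying only to a test that is itself Grade 3, the overlap shrinks to ALT/AST >5 to 8 with bilirubin >5 to 10, or ALT/AST >8 to 20 with bilirubin >3 to 5. Both boxes already exceed the Hy's-law thresholds (allowing ALT or AST), so on that reading a conflict remains only for patients with cholestasis or another cause. With *and* in the hold branch, no patient can satisfy both.

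**6. Frequency.** The documents give no rate for the combined elevation. The nearest figures, in section 2.2.2, are treatment-related Grade 3 or higher AST in 7 of 694 and ALT in 5 of 694 monotherapy patients in Study 1108. Scaled to this trial, 50 × 7/694 = 0.50 and 50 × 5/694 = 0.36 patients. These are higher-grade rises with or without raised bilirubin, so they indicate scale only and do not bound the Grade 2 rate.

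**The case against.** The best defence is that the documents already settle the matter. The stop is worded for all cases, 6.4 gives it force, and a specific binding stop outranks a general resume line. This stands: a reader who puts the two together stops the drug. A reader might infer that the protocol has no Hy's-law rule for Grade 2 patients, or that it directs their rechallenge. The text supports neither.

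The route to error is also narrow. These laboratory values trigger the 24-hour report, interruption when unexplained, and evaluation by sponsor and company. Section 8.1.6 requires someone to decide whether the case meets Hy's law, and the only dosing instruction naming Hy's law is the permanent stop. Holding first is right in any event, because the absence of another cause can be judged only after work-up. Doses are four weeks apart, any steroid taper lasts at least 28 days, and serious adverse events are reviewed monthly under section 13.1. All of this lowers the risk. What it does not do is state the outcome: interruption under 8.3.4.2 is compatible with later resumption, and the study-physician discussion is triggered only if the event has not resolved in 1 to 2 days.

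Two further points limit the criticism. The neuromotor rows might suggest that the table always repeats a cross-grade stop in each affected cell. It does not, as the steroid and bullous stops show. And although the Appendix D parenthesis names ALT only, the Hy's-law criteria printed after 8.1.11 use ALT or AST, which largely answers that mismatch.

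Section 7 also points to management guidelines in the Investigator's Brochure. I cannot check whether they address this.

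**Conclusion.** The point holds as a placement and cross-reference defect. The stop is universal in wording and binding through 6.4, but it sits in one grade's cell, and the Grade 2 row that shares its thresholds neither repeats it nor points to it. Table 1 gives its other cross-grade stops reviewed here either a general location or repetition in each affected grade; the Hy's-law stop has neither.

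The affected patients have ALT above 3 to 5 times and bilirubin above 2 to 3 times ULN, no initial cholestasis and no alternative cause. I expect few or none in 50 patients, which is a judgement rather than a calculation. The width of the threshold overlap says nothing about how many patients fall in it. The conclusion assumes that the Hy's-law sentence belongs to the Grade 3 cell. That cell crosses a page break, but the sentence comes before the Grade 4 row, so the reading is sound.

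The wording should be fixed because the possible error is serious and the correction is trivial. It has no bearing on sample size or the primary analysis. The Grade 3 branch overlap is real as printed and can be corrected in the same amendment.

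**What to change.** 1. Move the stop to the hepatitis Any Grade row of Appendix D, Table 1, worded to cover ALT or AST above 3 times ULN plus bilirubin above 2 times ULN, without initial cholestasis and without an alternative cause.
2. Add to the Grade 2 resume line: *unless Hy's law criteria are met*.
3. In 8.3.4.2, after the interruption instruction, add that if Hy's law criteria are met the drug is permanently discontinued, with a reference to Appendix D.
4. Separately, make the Grade 3 hold branch require transaminases ≤8 times *and* bilirubin ≤5 times ULN. Leave the discontinue branch as it is.

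The cost is a wording amendment to the hepatitis rows and one cross-reference. No procedures, visits or patients are added.

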6. TREATMENT PLAN

6.1 Durvalumab Administration

Treatment will be administered on an outpatient basis. No investigational or commercial agents or therapies other than those described below may be administered with the intent to treat the patient's malignancy.

Regimen Description					
Agent	Premedications / Precautions	Dose	Route	Schedule	Cycle Length
Durvalumab	N/A	** in 500 cc NS	IV over 60 minutes (± 5 minutes)	Day 1	28 days (4 weeks)

** Dose calculation is based in patient weight at the time of each treatment. See section 6.1.1 for fixed dose information for subjects weighing greater than or equal to 30 kg and Appendix C for calculation of dose for subjects with weight of less than 30 kg.

Study drug preparation

For patients weighing ≥ 30 kg, a fixed dose of 1500 mg Q4W durvalumab (equivalent to 20 mg/kg Q4W) (based on an average body WT of 75 kg) should be prepared. For subjects <30 kg body weight, dose is determined using body mass, calculating the stock volume of durvalumab to achieve the accurate dose according to Appendix C.

Preparation of durvalumab doses for administration with an IV bag

The dose of durvalumab for administration must be prepared by the Investigator's or site's designated IP manager using aseptic technique. Total time from needle puncture of the durvalumab vial to the start of administration should not exceed:

- 24 hours at 2°C to 8°C (36°F to 46°F)
- 4 hours at room temperature

If in-use storage time exceeds these limits, a new dose must be prepared from new vials. Infusion solutions must be allowed to equilibrate to room temperature prior to commencement of administration.

No incompatibilities between durvalumab and polyvinylchloride or polyolefin IV bags have been observed. Dose of 1500mg durvalumab for patients >30 kg will be administered using an IV bag containing 0.9% (w/v) saline or 5% (w/v) dextrose for IV infusion with a final durvalumab concentration ranging from 1 to 20 mg/mL, and delivered through an IV administration set with a 0.2- or 0.22- μm in-line filter.

Remove a volume of IV solution from the IV bag equal to the calculated volume of durvalumab to be added to the IV bag prior to addition of durvalumab. Next, the volume of durvalumab (i.e., 30.0 mL for 1500 mg of durvalumab) is added to the IV bag such that final concentration is within 1 to 20 mg/mL (IV bag volumes 100 to 1000 mL). Mix the bag by gently inverting to ensure homogeneity of the dose in the bag.

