7. DOSING DELAYS/DOSE MODIFICATIONS

For adverse events (AEs) that are considered at least partly due to administration of durvalumab, the following dose adjustment guidance may be applied:

- Treat each of the toxicities with maximum supportive care (including holding the agent suspected of causing the toxicity where required).
- If the symptoms promptly resolve with supportive care, consideration should be given to continuing the same dose of durvalumab along with appropriate continuing supportive care. If medically appropriate, dose modifications are permitted for durvalumab (see

HCC #:16-054

Version Date: 008/11/2020

below).

- All dose modifications should be documented with clear reasoning and documentation of the approach taken.

In addition, there are certain circumstances in which durvalumab should be permanently discontinued.

Following the first dose of durvalumab, subsequent administration of durvalumab can be modified based on toxicities observed (Appendix D).

Based on the mechanism of action of durvalumab leading to T-cell activation and proliferation, there is the possibility of observing immune related Adverse Events (irAEs) during the conduct of this study.

Immune-mediated reactions/irAEs, also considered to be AESIs, are important risks of immune checkpoint inhibitors, and are being closely monitored in clinical studies with durvalumab monotherapy and combination therapy. irAEs observed with durvalumab include colitis, pneumonitis, hepatitis/hepatotoxicity, neuropathy/neuromuscular toxicity, endocrinopathy, dermatitis, and nephritis. In addition, pancreatitis is an important potential risk, particularly with durvalumab and tremelimumab combination therapy.

Other inflammatory responses with potential immune-mediated etiology reported with durvalumab and similar molecules include, but are not limited to, myocarditis, pericarditis, and uveitis. Subjects should be monitored for signs and symptoms of irAEs. In the absence of an alternate etiology (e.g., infection or PD) signs or symptoms of the above events of interests should be considered to be immune-related.

- Dose modification recommendations and toxicity management guidelines for immune-mediated reactions, for infusion-related reactions, and for non-immune-mediated reactions are detailed in Tables 1, 2, and 3 of Appendix D, respectively.

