Grade 2	The infusion rate of study drug/study regimen may be decreased 50% or temporarily interrupted until resolution of the event. Subsequent infusions may be given at 50% of the initial infusion rate.	
Grade 3/4	Permanently discontinue study drug/study regimen	For Grade 3 or 4: Manage severe infusion-related reactions per institutional standards (e.g., IM epinephrine, followed by IV diphenhydramine and ranitidine, and IV glucocorticoid)

Table 3- Non-immune Mediated Reactions		
CTC Grade/Severity	Dose Modification	Toxicity Management
Any Grade	Note: dose modifications are not required for adverse events not deemed to be related to study treatment (i.e. events due to underlying disease) or for laboratory abnormalities not deemed to be clinically significant.	Treat accordingly as per institutional standard
1	No dose adjustment	Treat accordingly as per institutional standard

Table 3- Non-immune Mediated Reactions		
CTC Grade/Severity	Dose Modification	Toxicity Management
2	Hold study drug/study regimen until resolution to \leq Grade 1 or baseline	Treat accordingly as per institutional standard
3	Hold study drug/study regimen until resolution to \leq Grade 1 or baseline For AEs that downgrade to \leq Grade 2 within 7 days or resolve to \leq Grade 1 or baseline within 14 days, resume study drug/study regimen administration at next scheduled dose. Otherwise, discontinue study drug/study regimen	Treat accordingly as per institutional standard
4	Discontinue Study drug/study regimen (Note for Grade 4 labs, decision to discontinue would be based on accompanying clinical signs/symptoms and as per Investigator's clinical judgment and in consultation with the sponsor)	Treat accordingly as per institutional standard

Abbreviations:

AChE = acetylcholine esterase; ADA = American Dietetic Association; AE = adverse event; ALP = alkaline phosphatase; ALT = alanine aminotransferase; AST = aspartate aminotransferase; CT = computed tomography; GI = gastrointestinal; IDS=Infectious Disease Service; ILD = interstitial lung disease; IM = intramuscular; irAE = immune-related adverse event; IV = intravenous; NCI CTCAE = National Cancer Institute Common Terminology Criteria for Adverse Events; PO = by mouth; TNF = tumor necrosis factor; TSH = thyroid stimulating hormone; ULN = upper limit of normal.

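### Appendix D Table 3: for a non-immune Grade 3 event that falls to Grade 2 within 7 days and is still Grade 2 at the next dose, the Grade 3 row says both hold and resume

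*Combined protocol and SAP*

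**What the plan says.** Table 3 of Appendix D covers non-immune-mediated reactions, with one row per CTC grade.

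- **Grade 2 row:** "Hold study drug/study regimen until resolution to" Grade 1 or lower, or baseline. It has no time limit and no option to restart while the event is at Grade 2.
- **Grade 3 row, first sentence:** the same hold wording and the same end point as the Grade 2 row.
- **Grade 3 row, second sentence:** this follows directly in the same cell ("Grade 1 or baseline For AEs that downgrade to"). One arm is a fall to "Grade 2 within 7 days or resolve to" the second arm, which is "Grade 1 or baseline within 14 days, resume study drug/study regimen administration at next scheduled dose. Otherwise, discontinue study drug/study regimen".

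Two sections of the protocol body rely on this table. Section 7 states: "Following the first dose of durvalumab, subsequent administration of durvalumab can be modified based on toxicities observed (Appendix D"). Section 6.4 lists among the reasons for permanent discontinuation: "Any AE that meets criteria for discontinuation as defined in Appendix D". Neither says which sentence of the Grade 3 row governs. Section 6.1 sets the cycle length at "28 days (4 weeks"), which determines when the next scheduled dose falls.

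**The concern.** A single table cell attaches two different thresholds to restarting drug after a Grade 3 event. One is Grade 1 or baseline. The other is Grade 2, if reached within 7 days. Where an event satisfies the second but not the first, the physician has opposite instructions for the same patient on the same day.

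The neighbouring row adds to the difficulty. A patient whose event never went above Grade 2 must be held. A patient who has come down from Grade 3 to the same Grade 2 may, on one sentence, be dosed.

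What is at stake is consistent dosing. Two physicians could follow the table faithfully and one would re-dose while the other held. That is a patient-safety matter first. It also adds avoidable variation in exposure to a trial with safety as one of its two primary objectives.

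**Working it through.** The plan gives no figure to reproduce, and no sample size, power or event count is involved. The check runs each possible course of a non-immune Grade 3 event through the three statements. Baseline is taken to be below Grade 2 except in the last row, and days are counted from onset at Grade 3.

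| Course | Grade 3 row, sentence 1 | Grade 3 row, sentence 2 | Grade 2 row, if it applies to the current grade | Result |
|---|---|---|---|---|
| A. Grade 1 or lower by day 14 | hold over | resume | hold over | clear: resume |
| B. Grade 2 by day 7, still Grade 2 at next dose | hold | resume | hold | **conflict** |
| C. Grade 2 by day 7, Grade 1 or lower before next dose | hold over | resume | hold over | clear: resume |
| D. Still Grade 3 after day 7, not at Grade 1 or baseline by day 14 | hold, if read alone | discontinue | – | clear: the closing clause settles it |
| E. Baseline already Grade 2, back to Grade 2 by day 14 | hold over (baseline) | resume | hold over (baseline) | clear: resume |

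Only course B fails. The closing discontinuation clause does not settle it, because the two arms of the second sentence are joined by an or. An event at Grade 2 by day 7 has met the first arm, so it does not fall into the remainder that is discontinued.

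**Can course B arise without an unusually long event?** With a 28-day cycle dosed on day 1, the next dose is due on day 29. An event starting on cycle day *d* has 29 − *d* days until that dose.

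- Onset on day 22: 29 − 22 = 7 days. An event at Grade 2 by the seventh day and still Grade 2 at the visit is in course B.
- Onset on day 8: 29 − 8 = 21 days. An event reaching Grade 2 on its seventh day must stay there a further 21 − 7 = 14 days.

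The course therefore needs prolonged Grade 2 persistence when onset is early in the cycle, and little or none when onset is in the last week.

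**Do the documents break the tie?** The second sentence can be read in two ways:

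1. As a specific exception to the first sentence. Course B then resumes.
2. As deciding only between resuming and discontinuing once the hold has ended. Course B then stays on hold, and the Grade 2 arm can never by itself permit dosing.

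Nothing in Section 6.4, Section 7 or Appendix D chooses between them. Elsewhere in Appendix D a single threshold is used: the Grade 3 hepatitis row (lower elevations) and the Grade 3 rash row each keep the same grade condition for the hold and for what follows. That shows the cell can be written without conflict. It does not show which condition is meant in Table 3.

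**The case against.** The strongest reply is that a careful reader can make the table work. Rows are indexed by severity, and Section 8.3 records the maximum grade for each event. An event that peaked at Grade 3 could therefore stay in the Grade 3 row, with its own downgrade rule. On that reading the difference from the Grade 2 row is an asymmetry between rows, not a contradiction. This has force, and it is why the Grade 2 row counts here only on the condition that it applies to the current grade. It does not remove the conflict between the two sentences inside the Grade 3 row.

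A second reply is that Section 7 presents the appendix as guidance that may be applied, and that the study team meets monthly to discuss subject safety (Section 13.1). Both soften the problem. Neither tells a physician what to do on the dosing day, and Section 6.4 makes the appendix's discontinuation criteria operative.

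A reader might also infer a wider problem, which the documents do not support:

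- **Every Grade 3 event still at Grade 2 at the next visit is affected.** It is not. The 7-day condition, the baseline alternative and the closing clause remove all courses but B.
- **Permanent discontinuation is in doubt.** In course B the choice is between holding and resuming. The discontinuation clause is not reached.
- **The primary safety rate would shift.** Section 14.3 counts each related event once per patient at its highest grade. A course B patient with a related Grade 3 event is already in the numerator, whether then held or re-dosed.

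**Conclusion.** The Grade 3 row of Table 3 is wrong as written, but the fault is minor. It gives opposite instructions for one defined course: non-immune Grade 3 event, baseline below Grade 2, Grade 2 within 7 days, still Grade 2 at the next scheduled dose. The conclusion rests on the wording of that cell and on the absence of a governing statement elsewhere. It does not depend on how the Grade 2 row is read.

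The size cannot be stated, because the documents give no frequency for this course. It is tempting to use the related Grade 3 or higher rates in the background, 6% (Section 2.3) and 9.4% (Section 2.2.2), or the 30% tolerability limit in Section 14.3. None of these measures the problem. The first two are overall rates not restricted to non-immune Grade 3 events, let alone to course B, and the third is a benchmark for the primary endpoint. Any effect on exposure or on later events is indirect and cannot be quantified from the documents.

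**What to change.** Reconcile the two sentences of the Grade 3 row so that one resumption condition applies. State how that row relates to the Grade 2 row once a Grade 3 event has come down to Grade 2, that is, whether the row is chosen by peak grade or by current grade. Which condition applies is for the sponsor's clinical lead to decide; this review takes no position on it.

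The cost is a table-text correction. The sample size, endpoints and analysis plan are unchanged.
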